### **Publication Policy**

To coordinate dissemination of data from this study, Amgen may facilitate the formation of a publication committee consisting of several investigators and appropriate Amgen staff, the governance and responsibilities of which are set forth in a Publication Charter. The committee is expected to solicit input and assistance from other investigators and to collaborate with authors and Amgen staff, as appropriate, as defined in the Publication Charter. Membership on the committee (both for investigators and Amgen staff) does

not guarantee authorship. The criteria described below are to be met for every publication.

Authorship of any publications resulting from this study will be determined on the basis of the Uniform Requirement for Manuscripts Submitted to Biomedical Journals International Committee of Medical Journal Editors Recommendations for the Conduct of Reporting, Editing, and Publications of Scholarly Work in Medical Journals, which states: Authorship credit is to be based on: (1) substantial contributions to conception and design, or the acquisition, analysis, or interpretation of data for the work; (2) drafting the work or revising it critically for important intellectual content; (3) final approval of the version to be published; and (4) agreement to be accountable for all aspects of the work in ensuring that questions related to the accuracy or integrity of any part of the work are appropriately investigated and resolved. Authors need to meet conditions 1, 2, 3, and 4.

When a large, multicenter group has conducted the work, the group is to identify the individuals who accept direct responsibility for the manuscript. These individuals must fully meet the criteria for authorship defined above. Acquisition of funding, collection of data, or general supervision of the research group, alone, does not justify authorship. All persons designated as authors must qualify for authorship, and all those who qualify are to be listed. Each author must have participated sufficiently in the work to take public responsibility for appropriate portions of the content. All publications (eg, manuscripts, abstracts, oral/slide presentations, book chapters) based on this study must be submitted to Amgen for review. The Clinical Trial Agreement among the institution, investigator, and Amgen will detail the procedures for, and timing of, Amgen's review of publications.

### **Investigator Signatory Obligations**

Each clinical study report is to be signed by the investigator or, in the case of multicenter studies, the coordinating investigator.

The coordinating investigator, identified by Amgen, will be any or all of the following:

- A recognized expert in the therapeutic area
- An investigator who provided significant contributions to either the design or interpretation of the study
- An investigator contributing a high number of eligible subjects

## **Data Quality Assurance**

All subject data relating to the study will be recorded on printed or electronic CRF unless transmitted to the sponsor or designee electronically (eg, laboratory data, centrally or adjudicated data). The investigator is responsible for verifying that data entries are accurate and correct by physically or electronically signing the CRF.

The investigator must maintain accurate documentation (source data) that supports the information entered in the CRF.

The investigator must permit study-related monitoring, audits, IRB/IEC review, and regulatory agency inspections and provide direct access to source data documents.

The sponsor or designee is responsible for the data management of this study including quality checking of the data.

Clinical monitors will perform ongoing source data verification to confirm that data entered into the CRF by authorized site personnel are accurate, complete, and verifiable from source documents; that the safety and rights of subjects are being protected; and that the study is being conducted in accordance with the currently approved protocol and any other study agreements, ICH GCP, and all applicable regulatory requirements per the sponsor's monitoring plan.

The investigator agrees to cooperate with the clinical monitor to ensure that any problems detected in the course of these monitoring visits, including delays in completing CRFs, are resolved.

The Amgen representative(s) and regulatory authority inspectors are responsible for contacting and visiting the investigator for the purpose of inspecting the facilities and, upon request, inspecting the various records of the clinical study (eg, CRFs and other pertinent data) provided that subject confidentiality is respected.

In accordance with ICH GCP and the sponsor's audit plans, this study may be selected for audit by representatives from Amgen's Global Research and Development Compliance and Audit function (or designees). Inspection of site facilities (eg, pharmacy, protocol-required therapy storage areas, laboratories) and review of study-related records will occur to evaluate the study conduct and compliance with the protocol, ICH GCP, and applicable regulatory requirements.

Quality tolerance limit parameters (QTLs) will be predefined in the QTL definitions table to identify possible systematic issues that can impact participant safety and/or reliability

of the study results. These predefined parameters will be monitored during the study. Important deviations from the QTL threshold limits for these parameters and remedial actions taken will be summarized in the clinical study report.

Retention of study documents will be governed by the Clinical Trial Agreement.

Case Report Forms (CRF) must be completed in English. TRADENAMES® (if used) for concomitant medications may be entered in the local language. Consult the country-specific language requirements.

All written information and other material to be used by subjects and investigative staff must use vocabulary and language that are clearly understood.

### **Source Documents**

The investigator is to maintain a list of appropriately qualified persons to whom he/she has delegated study duties. All persons authorized to make entries and/or corrections on CRFs will be included on the Amgen Delegation of Authority Form.

Source documents provide evidence for the existence of the subject and substantiate the integrity of the data collected. Source documents are filed at the investigator's site.

Source documents are original documents, data, and records from which the subject's CRF data are obtained. These include but are not limited to hospital records, clinical and office charts, laboratory and pharmacy records, diaries, microfiches, radiographs, and correspondence. Source documents may also include data captured in the IRT system (if used, such as subject ID and randomization number) and CRF entries if the CRF is the site of the original recording (ie, there is no other written or electronic record of data, such as paper questionnaires for a clinical outcome assessment or certain demographic information, such as gender, race, and ethnicity).

Data reported on the CRF or entered in the electronic CRF that are transcribed from source documents must be consistent with the source documents or the discrepancies must be explained. The investigator may need to request previous medical records or transfer records, depending on the study. Also, current medical records must be available.

The investigator and study staff are responsible for maintaining a comprehensive and centralized filing system of all study-related (essential) documentation, suitable for inspection at any time by representatives from Amgen and/or applicable regulatory authorities.

Elements to include:

- Subject files containing completed CRFs, informed consent forms, and subject identification list
- Study files containing the protocol with all amendments, IB, copies of prestudy documentation, and all correspondence to and from the IRB/IEC and Amgen
- Investigational product-related correspondence including Proof of Receipts, Investigational Product Accountability Record(s), Return of Investigational Product for Destruction Form(s), Final Investigational Product Reconciliation Statement, as applicable
- Non-investigational product(s), and/or medical device(s) or combination product(s) documentation, as applicable

Retention of study documents will be governed by the Clinical Trial Agreement.

### **Remote Source Data Review and Verification**

If permitted by national and/or local regulations, remote Source Data Review and Verification (rSDR/V) can be implemented. The clinical monitor should be provided with a secure, read-only access to the Electronic Medical Record (EMR) system, including all modules relevant for review. This access should be restricted to the records of only those patients who participate in the trial and who did not object to remote access to their medical records. A list of the monitors to whom remote access has been granted should be maintained. In order to prevent unauthorized access, access rights should be revoked once rSDR/V tasks have been completed for the trial. The EMR system should have an audit trail and be able to log information on who accessed data and when.

Remote access to the EMR should only be possible using a two-factor authentication.

### **Study and Site Closure**

Amgen or its designee may stop the study or study site participation in the study for medical, safety, regulatory, administrative, or other reasons consistent with applicable laws, regulations, and GCP.

Both Amgen and the investigator reserve the right to terminate the investigator's participation in the study according to the Clinical Trial Agreement. The investigator is to notify the IRB/IEC in writing of the study's completion or early termination and send a copy of the notification to Amgen.

Subjects may be eligible for continued treatment with Amgen investigational product(s) by a separate protocol or as provided for by the local country's regulatory mechanism. However, Amgen reserves the unilateral right, at its sole discretion, to determine

whether to supply Amgen investigational product(s) and by what mechanism, after termination of the study and before the product(s) is/are available commercially.

### **Compensation**

Any arrangements for compensation to subjects for injury or illness that arises in the study are described in the Compensation for Injury section of the Informed Consent that is available as a separate document.

## **11.4 Appendix 4. Safety Events: Definitions and Procedures for Recording, Evaluating, Follow-up and Reporting**

### **Definition of Adverse Event**

Adverse Event Definition

• An adverse event is any untoward medical occurrence in a clinical study subject irrespective of a causal relationship with the study treatment.

• Note: An adverse event can therefore be any unfavorable and unintended sign (including an abnormal laboratory finding), symptom, or disease (new or exacerbated) temporally associated with the use of a treatment, combination product, medical device or procedure.

• Note: Treatment-emergent adverse events will be defined in the Statistical Analysis Plan (SAP).

Events Meeting the Adverse Event Definition


• Any abnormal laboratory test results (hematology, clinical chemistry, or urinalysis) or other safety assessments (eg, ECG, radiological scans, vital signs measurements), including those that worsen from baseline, that are considered clinically significant in the medical and scientific judgment of the investigator (ie, not related to progression of underlying disease).

• Exacerbation of a chronic or intermittent preexisting condition including either an increase in frequency and/or intensity of the condition.

• New conditions detected or diagnosed after study treatment administration even though it may have been present before the start of the study.

• Signs, symptoms, or the clinical sequelae of a suspected drug-drug interaction.

• Signs, symptoms, or the clinical sequelae of a suspected overdose of either study treatment or a concomitant medication. Overdose per se will not be reported as an adverse event/serious adverse event unless it is an intentional overdose taken with possible suicidal/self-harming intent. Such overdoses are to be reported regardless of sequelae.

• For situations when an adverse event or serious adverse event is due to mCRPC report all known signs and symptoms. Death due to disease progression in the absence of signs and symptoms should be reported as the primary tumor type (eg, metastatic pancreatic cancer). Note: The term “disease progression” should not be used to describe the adverse event.

• “Lack of efficacy” or “failure of expected pharmacological action” per se will not be reported as an adverse event or serious adverse event. Such instances will be captured in the efficacy assessments. However, the signs, symptoms, and/or clinical sequelae resulting from lack of efficacy will be reported as adverse event or serious adverse event if they fulfill the definition of an adverse event or serious adverse event.

Events NOT Meeting the Adverse Event Definition

• Medical or surgical procedure (eg, endoscopy, appendectomy): the condition that leads to the procedure is the adverse event.

- Situations in which an untoward medical occurrence did not occur (social and/or convenience admission to a hospital).
- Anticipated day-to-day fluctuations of preexisting disease(s) or condition(s) present or detected at the start of the study that do not worsen.

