#### **2.2.4.3 Clinical Data**

The safety, tolerability, PK, and clinical activity of AMG 340 are currently being evaluated in this ongoing phase 1, open-label, dose-escalation and expansion study of AMG 340 in subjects with mCRPC. As of the safety data cutoff date of 08 March 2022, a total of 24 subjects were enrolled in the study; 1 subject did not receive investigational product. In cohort 5, a single grade 3 CRS event was observed that triggered the implementation of a priming dose per protocol Section 6.2.1.2.

All 23 subjects who received at least 1 dose of investigational product had a treatment emergent adverse event (defined as events that occurred or worsened on or after the first dose of AMG 340 until 90 days after discontinuation of AMG 340 or until the subject started another anticancer therapy, whichever occurred earlier). The most frequently reported adverse events ( $\geq 20\%$  of subjects) were nausea (13 subjects, 56.5%), vomiting (12 subjects, 52.2%), CRS (9 subjects, 39.1%), diarrhea (8 subjects, 34.8%), hypocalcemia (8 subjects, 34.8%), hypomagnesemia (7 subjects, 30.4%), dysgeusia (6 subjects, 26.1%), and hypophosphatemia (5 subjects, 21.7%). Eight subjects (34.8%) had at least 1 grade  $\geq 3$  adverse events. Grade 3 adverse events include anemia (3 subjects, 13.0%), aspartate aminotransferase increased (2 subjects, 8.7%), and thrombocytopenia, alanine aminotransferase increased, neutrophil count decreased, cytokine release syndrome, brain abscess, failure to thrive, confusional state, hydronephrosis, and hypoxia (each 1 subject, 4.3%). One subject (4.3%) had a grade 4 adverse events of neutropenia and thrombocytopenia, and 1 subject (4.3%) had a fatal adverse event of hemorrhage (cerebral hemorrhage following a fall).

One subject (4.3%) had an adverse event leading to discontinuation of AMG 340 (grade 2 cerebrovascular accident). Eight subjects (34.8%) had serious adverse events, including cytokine release syndrome (2 subjects, 8.7%), aspartate aminotransferase increased (2 subjects, 8.7%), and alanine aminotransferase increased, thrombocytopenia, brain abscess, failure to thrive, cerebrovascular accident, hematuria, and hemorrhage (cerebral hemorrhage following a fall) (each 1 subject, 4.3%). One subject had DLT events of neutropenia and thrombocytopenia.

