#### **6.2.1.4.1 Dose Limiting Toxicity Definition for Dose Escalation**

The DLT observation period for dose escalation purposes is 21 days and covers the first complete treatment cycle of AMG 340 (1 dose of AMG 340; or up to 3 doses if priming has been implemented). Regular teleconferences will be conducted among the DLRT to examine/confirm potential DLTs, assess adverse events, and evaluate laboratory abnormalities. Events occurring outside the DLT window may be evaluated during these calls when making dose escalation decisions. A DLT is defined as a treatment emergent adverse event that is not unequivocally due to the subject's underlying malignancy or other extraneous cause and meets the criteria below.

The NCI-CTCAE version 5.0 will be used. DLT definitions are provided below.

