##### **8.4.3 Clinical Laboratory Assessments**

Refer to Section 11.2 for the list of clinical laboratory tests to be performed and to the Schedule of Activities (Section 1.3) for the timing and frequency.

The investigator is responsible for reviewing laboratory test results and recording any clinically relevant changes occurring during the study in the Events CRF. The investigator must determine whether an abnormal value in an individual study subject represents a clinically significant change from the subject's baseline values. In general, abnormal laboratory findings without clinical significance (based on the investigator's judgment) are not to be recorded as adverse events. However, laboratory value changes that require treatment or adjustment in current therapy are considered adverse

events. Where applicable, clinical sequelae (not the laboratory abnormality) are to be recorded as the adverse event.

All protocol-required laboratory assessments, as defined in Section [11.2](#), must be conducted in accordance with the laboratory manual and the Schedule of Activities ([Table 1-1](#)).

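### Appendix 4 lets an abnormal laboratory result be left out of the adverse events as progression-related, a looser test than the DLT rule and one that applies first

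*Protocol*

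**What the plan says.** Protocol Section 11.4 (Appendix 4) opens with a definition that does not depend on cause: "An adverse event is any untoward medical occurrence in a clinical study subject irrespective of a causal relationship with the study treatment". Its note names laboratory values, covering "any unfavorable and unintended sign (including an abnormal laboratory finding), symptom, or disease (new or exacerbated").

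The list of events that meet the definition then narrows this for laboratory and other safety results, which count when "considered clinically significant in the medical and scientific judgment of the investigator (ie, not related to progression of underlying disease"). A later bullet in the same list points the other way: "For situations when an adverse event or serious adverse event is due to mCRPC report all known signs and symptoms".

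Section 8.4.3 has its own rule, with no condition on attribution: "laboratory value changes that require treatment or adjustment in current therapy are considered" adverse events. It also says that abnormal findings the investigator judges not clinically significant are generally not recorded.

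Section 6.2.1.4.1 builds the DLT on the adverse event: "A DLT is defined as a treatment emergent adverse event that is not unequivocally due to the" subject's cancer or some other outside cause, and that meets the listed criteria. SAP Section 5.1.1 likewise has investigators decide whether a treatment-emergent adverse event qualifies as a DLT.

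**The concern.** Two attribution tests act on the same laboratory value, one after the other. The recording test in Appendix 4 drops a value that is related to progression. The DLT test drops a value only when the attribution is certain. The looser test comes first, so the stricter one may never be applied to a doubtful case.

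This matters because DLTs are the endpoint for the MTD/RP2D objective and the input to the BOIN rule. Grade 4 neutropenia lasting more than 5 days, grade 4 thrombocytopenia and grade 4 anemia are DLT criteria that rest on laboratory values (Section 6.2.1.4.1.2). Some grade 3 chemistry values can also qualify (Section 6.2.1.4.1.1). The one DLT subject described so far had events of this kind: "One subject had DLT events of neutropenia and thrombocytopenia" (Section 2.2.4.3). Entry requires disease progression on the most recent therapy (criterion 105), so the cancer is a ready explanation for an abnormal value, and the study is open-label.

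**Working it through.** **1. The provisions side by side**

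| Provision | What it covers | Attribution condition |
|---|---|---|
| Appendix 4, general definition | Any untoward occurrence, laboratory findings named | None |
| Appendix 4, laboratory bullet | Clinically significant abnormal results | Must not be related to progression |
| Appendix 4, mCRPC bullet | Events due to the cancer | Signs and symptoms reported all the same |
| Section 8.4.3 | Laboratory changes needing treatment or a change in therapy | None |
| Appendix 7, reporting | AST or ALT raised together with bilirubin and/or INR | Reported as serious before the cause is worked up |
| Section 6.2.1.4.1 | Treatment-emergent adverse events meeting DLT criteria | Excused only if attribution elsewhere is certain |

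**2. Where the two tests differ.** Sort DLT-level laboratory values by the investigator's view: (a) not related to progression, (b) related but not certainly so, (c) certainly due to the cancer. The DLT rule removes (c). The laboratory bullet, read literally, removes (b) and (c). The exposed group is (b).

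**3. How much of (b) is caught elsewhere.**
- Section 8.4.3 catches values that lead to treatment or a change in therapy. In an unprimed 21-day cycle, a cytopenia that recovers untreated before cycle 2 day 1 need not change any dose. For such a value Section 8.4.3 falls back on clinical significance, the term that Appendix 4 defines by cause.
- The withholding rule for severe cytopenias in Section 6.2.1.4 sits under a lead-in about treatment-emergent adverse events not certainly due to the cancer. Read in that place, it presupposes an adverse event.
- Appendix 7 catches concurrent liver-test elevations, not an isolated transaminase rise.
- Section 6.2.1.4 has the investigator evaluate all laboratory abnormalities, but applies CTCAE grades to those reported as adverse events. DLT criteria are grade-based.
- Section 6.2.1.4.1 and Appendix 3 put laboratory results before the Dose Level Review Team. Neither says that an abnormality not recorded as an adverse event becomes one.

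What remains is (b) with no treatment, no therapy change and no concurrent liver trigger.

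**4. Effect of one missed DLT.** With target φ = 0.30 and assumed φ1 = 0.6φ = 0.18, φ2 = 1.4φ = 0.42:
- λe = ln(0.82/0.70) / ln[(0.30 × 0.82)/(0.18 × 0.70)] = 0.2365
- λd = ln(0.70/0.58) / ln[(0.42 × 0.70)/(0.30 × 0.58)] = 0.3585

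These agree with the stated 0.236 and 0.358, and all ten columns of Table 4-1 are reproduced. Reading the table:
- n = 3 (escalate at 0, de-escalate at 2 or more): 1 recorded as 0 turns stay into escalate.
- n = 6 (escalate at 1 or fewer, de-escalate at 3 or more): 2 recorded as 1 turns stay into escalate; 3 recorded as 2 turns de-escalate into stay.

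**5. Illustration only.** Assume a true DLT rate p and that each DLT is missed independently with probability f. The recorded count is then Binomial(6, p(1 − f)).

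| p | f | Recorded rate | P(escalate), ≤ 1 | P(de-escalate), ≥ 3 |
|---|---|---|---|---|
| 0.40 | 0 | 0.40 | 0.233 | 0.456 |
| 0.40 | 0.10 | 0.36 | 0.301 | 0.373 |
| 0.40 | 0.25 | 0.30 | 0.420 | 0.256 |
| 0.40 | 0.50 | 0.20 | 0.655 | 0.099 |

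For example, at f = 0.25: P(escalate) = 0.70^6 + 6 × 0.30 × 0.70^5 = 0.420. At p = 0.30 the four escalation probabilities are 0.420, 0.487, 0.594 and 0.776; at p = 0.45 they are 0.164, 0.226, 0.343 and 0.594.

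The documents give neither p nor f. Here f applies to all DLTs, whereas the gap concerns only the subset in step 3.

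**The case against.** The bullet belongs to a list of what counts as an adverse event. The separate list of what does not count has three items, and a progression-related laboratory result is not among them. The mCRPC bullet, read with a definition of sign that includes laboratory findings, arguably makes such results reportable. Section 8.4.3 and Appendix 7 are independent routes to recording, and the Dose Level Review Team evaluates laboratory abnormalities separately from adverse events. Entry limits on neutrophils, platelets, hemoglobin, bilirubin and transaminases (criteria 108 and 110), and a first scheduled on-treatment scan at cycle 3 day 1 (day 2 × 21 + 1 = 43, after the 21-day window), make it harder to blame progression for a DLT-level value. Cytopenias and transaminase rises have been recorded as adverse events in the 23 treated subjects, including the DLT subject.

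Much of this stands. A reader might infer that progression-related laboratory results are never recorded, never reach the DLT test, or are hidden from the Dose Level Review Team. The provisions just listed do not support that. Nor are all hematologic DLTs laboratory-based: the list also includes CRS, TLS and grade 5 events.

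The contradiction itself is not answered. The gloss gives a site a written reason not to record a doubtful case, and the other provisions leave part of that group uncovered. The events recorded so far show that capture works in some cases; they cannot show that nothing was left out.

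**Conclusion.** The point holds as an internal contradiction with a possible leak at the recording step. The laboratory gloss in Appendix 4 conflicts with three other recording provisions and sets a looser attribution test than the DLT rule it feeds. The events most exposed are DLT-level laboratory abnormalities judged related, but not certainly due, to progression that need no treatment or therapy change and do not meet the concurrent liver-test rule.

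The direction is certain: a missed DLT can only lower the observed rate, and one is enough to change a Table 4-1 decision at 1/3, 2/6 or 3/6. The frequency is unknown. A reader might take the probabilities above as an estimate of bias in the MTD. They are not, because they rest on an assumed true rate and assumed missed fractions of all DLTs. The change is worth making because the wording affects an input to a primary objective and is cheap to repair. Confidence is moderate, given the backstops.

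**What to change.** In the laboratory bullet of Appendix 4, delete the parenthesis that equates clinical significance with absence of a link to progression. State instead that a laboratory or other safety result that is clinically significant, or that needs treatment or a change in therapy as in Section 8.4.3, is recorded as an adverse event whatever its suspected cause. Add that the attribution judgement in Section 6.2.1.4.1 is then made on recorded events.

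This is a change to one bullet and leaves the DLT criteria and dosing rules as they are. The cost is some additional adverse event records that prove to be disease-related.
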